### 5. ASSESSMENT OF SAFETY

This is a low risk study which involves a widely-used CE-marked device. The patients will continue to see their GP, continue to receive the usual care and normal medication throughout the period of the intervention.

There is a low risk of skin itching in small percentage of participants who may be allergic to the pads of the TENS, and their skin may become red and irritated. Therefore, hypoallergenic electrode pads will be used for all participants. Participant will be withdrawn from the study in the unlikely event that they experience a SAR related to the medical device. All interventions and assessments including standard treadmill protocol and safety precaution will be adhered to and provided by trained and qualified individuals. A designated phone number of the CRF will be given to the patients to dial in case of any complaint during the office hours.

There is a very low risk that participants will develop a skin reaction to the adhesive in the strip used to attach the activPAL3 device to the thigh. The attachments used are all hypoallergenic and medical grade to minimize this possibility. The participants will be given a contact number of the research team to call if they have any concerns and are told to remove the device if they encounter any skin irritation. Some of the older participants may have fragile skin, with a very low risk of skin degradation when wearing or removing the monitor. The participants will be trained in appropriate removal of the waterproof dressing and monitor. The PrEPAID team has considerable expertise in the use of activPAL monitors, including extended use in a frail older adult population.

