### 3.5 Retention Rates

The study is an intention to treat analysis and therefore if a patient does not apply the TENS or attend the education class (if randomised to this arm) they will continue to be followed up. However, all participants will have the right to withdraw from the study at any stage. If willing the reasons for withdrawal will be documented and any data already collected from that participant will be analysed.

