**Visit 5- Follow-up Assessment Visit (3-months post-intervention):**

All participants recruited within first eight months of recruitment will be invited to return for a 3-month follow-up visit. Outcome assessments and procedure followed in Visits 1 and 4 will be repeated including questionnaires, treadmill protocol, blood sample collection and fitting of activPAL. The treadmill test will be by the investigators who are blinded to the participants group allocation. Participants will be given a prepaid envelope to return activPAL. We shall allow assessment visit window of  $\pm$  2 weeks.

Follow-up Assessment Visit (70 mins)	Time (mins)	Responsible

Complete questionnaires:
 
 
1. Generic quality of life questionnaire (SF-36)
 
2. Intermittent Claudication Questionnaire (ICQ)
 
3. Visual Analogue Scale (VAS)
 
4. Geriatric Depression Scale (Short Form) (GDS-SF)
 
5. Pain Self-Efficacy Questionnaire (PSEQ)
 
6. Illness Perception Questionnaire (IPQ)
 
 
If participant is exiting the study at this point:
 
 
7. TENS feedback questionnaire
 
	20	UA/JB
Treadmill protocol • MPQ (5 minutes post-treadmill protocol)	20	
Fitting of ActivPAL to participants and instruction for use	20	
Taking of blood sample	10	

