### **8.7 Sample size**

For the primary outcome measure, at 80% power and a two-tailed 5% significance level, 16 participants per group will allow detection of an effect size of 1.0 standard deviations of ACD in active TENS group compared to placebo control. Attrition rates in our previous pilot studies ranged from 7.1% to 10% . We will recruit 20 participants in each group, allowing for 20% attrition, and therefore aim to recruit 80 patients. If this effect size were applied to our separate pilot studies, this would provide the ability to detect a change of 169m (TENS) or 322m (SEDRIC) in our primary outcome measure of ACD. Indeed, in these studies, a sample size of 20 per group (TENS) and 14 per intervention group (SEDRIC) was sufficient to detect a significant difference in this outcome measure.

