#### **14.2 Informed consent**

Written informed consent shall be obtained from each trial participant. The Research Nurse will explain the exact nature of the study in writing, provision of patient information sheet, and verbally and will be responsible for consenting the participants. Trial participants will be informed that they are free to withdraw their consent from the study or study treatment at any time.

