Trial design:

We will conduct a 2 x 2 parallel group (TENS versus placebo TENS x SEDRIC versus no additional education) feasibility RCT to compare use of TENS against placebo TENS with and without a patient-centred education programme. Permuted block randomisation will be implemented to allocate patients to trial arms. The intervention will last for 6 weeks, and patients recruited within the first eight months will be further followed up for 3 months. Outcomes assessments will be implemented at baseline, after six weeks treatment and at 3 months follow up. We will collect information regarding the recruitment rate, intervention uptake, outcome measure completion rate, attrition rate, blinding fidelity, efficacy related to the primary, secondary and other PROMs, and patients experience of intervention including acceptability and ease of intervention.

Randomisation:

A central randomisation facility (interactive voice response system, IVRS) will allocate the randomised therapy per patient. The IVRS, based at the Data Centre, will be available by telephone. Stratified permuted block randomization procedures will be utilised to allocate patients to groups (Patients allocation will be stratified by gender and age, ABPI values). Permuted block design (PBD) will be used to allocated patients to the PE+TENS, PE+Placebo TENS, TENS, Placebo TENS using 4-way randomisation throughout the whole time until the recruitment of a minimum of 20 subjects in the each of the larger comparison groups are achieved.

Sample size:

Details regarding sample size calculation can be found in section 8.7 of the full study protocol (version 2.0). Summarily, 16 participants per group will allow detection of an effect size of 1.0sd of ACD in active TENS group compared to placebo control. Allowing for 20% attrition, we will recruit 20 participants in each group, and therefore aim to recruit 80 patients.

Framework

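### A device-related SAR takes the participant out of the study, not just off the device, which is not reconciled with the intention-to-treat follow-up rule

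*Protocol*

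**What the plan says.** Protocol section 5 (Assessment of Safety) gives a mandatory rule: "Participant will be withdrawn from the study in the unlikely event that they experience a SAR related to the medical device". It says nothing about stopping the device while keeping the participant under observation.

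Protocol section 3.5 (Retention Rates) describes the study as intention to treat. A participant who "does not apply the TENS or attend the education class (if randomised to this arm) they will continue to be followed up". The only withdrawal it describes is the participant's own choice, after which "any data already collected from that participant will be analysed". It does not mention the section 5 rule.

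Elsewhere the documents separate leaving treatment from leaving the study. Protocol section 14.2 says "Trial participants will be informed that they are free to withdraw their consent from the study or study treatment at any time". SAP Section 5 analyses withdrawal from intervention and from follow-up as distinct levels, and SAP Table 2 has a row of reasons for each. Neither says which level a SAR triggers.

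On timing, the SAP trial design paragraph says "Outcomes assessments will be implemented at baseline, after six weeks treatment and at 3 months follow up". The last of these applies to a subgroup only, under Visit 5 in the protocol: "All participants recruited within first eight months of recruitment will be invited to return for a 3-month follow-up visit".

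**The concern.** Under intention to treat, an event after randomisation that stops treatment should not by itself stop outcome measurement. Section 5 does stop it, and by rule rather than by the participant's choice. Removing the device ends the exposure to the device; ending every questionnaire, blood sample and walking test is not needed for that purpose.

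The loss would be of outcome data that could have been obtained. Change in ACD is the primary efficacy analysis, and outcome completion is one of the feasibility objectives. A participant removed under this rule would count as not completing outcomes for a reason unrelated to willingness or ability to attend. The wording could also be carried unchanged into the definitive trial.

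**Working it through.** **1. Do the two sections conflict?** Section 3.5 covers non-use of the intervention and voluntary withdrawal. Section 5 covers a device-related SAR. The triggers differ, so there is no flat contradiction. But a participant who stops TENS after a SAR is also no longer applying TENS. Section 3.5 would then keep that participant in follow-up and section 5 would not. No text in either document says which prevails or labels section 5 an exception.

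**2. What does the rule remove?** TENS, active or placebo, is used for six weeks (protocol section 4) in all four arms. Visit 4, at the end of those weeks, is the first post-baseline outcome assessment.

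| Time of SAR | Recruited in first eight months | Recruited later |
|---|---|---|
| During TENS use | 2 of 2 post-baseline assessment visits lost (Visits 4 and 5) | 1 of 1 lost (Visit 4) |
| Recognised only after Visit 4 | Visit 5 only | none |

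In the first row the data already collected contain baseline ACD but no later value, so no change in ACD exists. No sentence literally cancels Visits 4 and 5. Their loss is the plain meaning of being withdrawn from the study, and nothing provides for continued visits.

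**3. What is not lost?** Adverse events are to be followed up (protocol section 2.2) and summarised (section 8.5). Reasons and timing of withdrawal are reported (SAP Section 5 and Table 2). The SAP places the blinding and TENS acceptability questions at the point of exit.

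**4. The plan's sample size, reproduced.** Inputs from protocol section 8.7: effect 1.0 SD, 80% power, two-sided 5%, 20% attrition.

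- n per group = 2 × (1.96 + 0.8416)² / 1.0² = 15.7, rounded up to 16 (power 0.807 at 16).
- 16 / (1 − 0.20) = 20 per group, and 4 × 20 = 80.
- The exact t-test gives 16.7, so 17 per group (power 0.781 at 16).

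**5. Can the attrition allowance absorb a case?** Section 8.7 says "We will recruit 20 participants in each group, allowing for 20% attrition, and therefore aim to recruit 80 patients", and puts pilot attrition at 7.1% to 10%.

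- Allowance per arm: 20 − 16 = 4.
- Pilot attrition applied to 20: 20 × 0.071 = 1.42 and 20 × 0.10 = 2.0.
- One SAR on top of 10% attrition: 20 − 2 − 1 = 17, which is at least 16.

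**6. How often?** The documents give no SAR rate. For scale only, assume a rate r per participant: expected cases among 80 are 80r, and the chance of at least one is 1 − (1 − r)^80.

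| Assumed r | Expected of 80 | Chance of at least one |
|---|---|---|
| 0.5% | 0.4 | 33% |
| 1% | 0.8 | 55% |
| 2% | 1.6 | 80% |
| 5% | 4.0 | 98% |

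These rates are assumptions, not estimates. Section 7.3 anticipates no serious events from the device, so the true number may be zero.

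**The case against.** The strongest reply is that section 5 is a deliberate and narrow safety exception. A specific safety rule beside a general follow-up rule is ordinary drafting. The authors distinguish study from study treatment elsewhere, and may have chosen the wider word on purpose. If SAR means a serious adverse reaction, the participant has just had an event meeting a section 7.2 criterion. The primary outcome is a treadmill walk to the limit of tolerance, and section 5 itself accepts a small chance that "participants will develop a skin reaction to the adhesive in the strip used to attach the activPAL3 device to the thigh". Stopping TENS does not remove the risks of those assessments. The event is also described as unlikely, and the attrition allowance covers it.

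Much of this stands. The sections do not contradict each other, the exception may be intended, the event should be rare, and ACD may not be recoverable in every case. What does not follow is that every assessment must end. Questionnaires and a blood sample do not involve the TENS device, and the safety of the treadmill test and the activPAL can be judged case by case. An allowance for unavoidable losses is no reason to discard data that could be obtained. If an exception is intended, it should be stated as one.

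**Conclusion.** The concern holds as a minor point. Followed as written, the rule removes every post-baseline assessment of a participant who has a device-related SAR during TENS use, and the plan does not reconcile this with its own intention-to-treat follow-up rule. The number of participants affected cannot be estimated from the documents. No effect on power, retention percentage or arm means is claimed, and the case would be visible among the withdrawal reasons.

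Two assumptions support this. The first is that withdrawal from the study ends the scheduled visits. The second is that SAR means serious adverse reaction: the term is not in the protocol's abbreviations list, and section 7 defines only adverse events and serious adverse events.

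**What to change.** Replace the sentence in protocol section 5 with wording such as:

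> TENS will be discontinued in a participant who has a serious adverse reaction related to the device (one meeting a criterion in section 7.2). The event will be followed to resolution. Scheduled outcome and safety assessments will continue where the investigator judges each one clinically safe, including the treadmill test and the activPAL adhesive, unless the participant withdraws consent.

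In SAP Table 2, report such a case as withdrawal from intervention, and as withdrawal from follow-up only if follow-up also stops.

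The cost is one protocol sentence through the usual amendment route, a safety judgement for each case, and one or two more visits for the participant. Recovery may be partial: where the treadmill test and activPAL are judged unsafe, only the questionnaires and blood sample would be obtained.

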### 6. DEVICE INFORMATION

Patients who are eligible for the study will be randomised to receive either active TENS or Placebo TENS.

#### 6.1 Active TENS:

A MTR+ Dolito TENS machine (EME Service Ltd., Manchester, United Kingdom) calibrated to 120Hz, 200 $\mu$ s, and patient-determined intensity of “strong but comfortable.”

##### 6.1.1 Treatment schedule:

Participants will be asked to wear active TENS everyday as often as they can when they are awake and switch it on when they are standing/ walking or about to engage in activity which they anticipate would trigger their IC pain. They will be instructed to switch it off after a maximum period of 1hr, for a rest period of at least 10-20 minutes, and to repeat this as often as warranted during daily activity.

##### 6.1.2 Rationale for chosen TENS frequency:

In a proof of concept study, HF-TENS was found to increase the distance IC patients walked before reaching pain tolerance, and that HF-TENS (compared to low frequency TENS) was more effective at prolonging the time to reach pain threshold.

##### 6.1.3 Attachment:

Patients will fit a TENS unit during wake periods and daily activity using 2 self-adhesive carbon rubber electrodes measuring 5 x 5 cm (StiMus® Hydrogel Premium

Self-Adhesive Electrodes, EME Service Ltd., Manchester, United Kingdom) attached to the TENS unit via the manufacturers leads. The area of pain reported by the participant would determine the electrode placement sites with the 2 electrodes to be placed at least 2cm apart. Before it is handed out to the patients for daily use, the TENS machine will be calibrated with a digital oscilloscope and tested manually by the research team.

## 6.2 Placebo TENS:

Placebo effect has been reported while using TENS in other conditions therefore, testing active TENS against placebo is advocated. The same model as used in active TENS will be used in the placebo TENS group but an infective setting (current intensity of about 6mA) will be used. Patients will be told that different doses of TENS are being tested. This will allow the unit to be switched on with the appearance of a working unit. All TENS units will be calibrated, checked and confirmed prior to being issued to participants. This method of achieving placebo has been successfully used in previous TENS trials.

### 6.2.1 Treatment schedule:

Participants will be asked to wear placebo TENS everyday as often as they could when they are awake and switch it on when they are standing/ walking or about to engage in activity which they anticipate would trigger their IC pain. They will be instructed to switch it off after a maximum period of 1hr, for a rest period of at least 10-20 minutes, and to repeat this as often as warranted during daily activity.

### 6.2.2 Attachment:

The same material will be used and similar instruction related to device attachment will be similar as active TENS.

## 7.0 ADVERSE EVENTS

### 7.1 Definitions of adverse events

**Adverse Event (AE)** – Any untoward medical occurrence in a subject to whom a medicinal device has been administered, including occurrences which are not necessarily caused by or related to that product.

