### Interventions:

**TENS:** Participants will be given TENS at intervention visit. They will be instructed to use the device daily at home or elsewhere. They will be specifically advised to use the device prior to, or during, a challenging walk each day. Challenging walk could be for activities of daily living (ADL) or planned exercise. For those with bilateral claudication they are advised to wear the device on the worst limb and could alternate it as symptoms fluctuates. The active group will receive High Frequency-TENS (120 Hz, 200µs and a patient-determined intensity of “strong but comfortable”).

**Placebo TENS:** Participants will receive the same model and instructions for use as those in the active group except that the stimulation dose is be safely altered to produce non-therapeutic, ineffective stimulation. For the purposes of blinding, participants will be told that different dosages of TENS are being tested some of which they might not feel anything even though the device is working. This method of effecting placebo has been successfully used in previous TENS trials.

Both the statistician conducting the randomization and the outcome assessor would be blinded to active TENS and placebo TENS. Importantly, participants will receive the same set of instructions as those in active TENS with the addition of a statement that two TENS are being tested. Blinding will be assessed at the end of the intervention period. Participants will be asked if they believed their TENS unit was functioning properly.

**Patient-Centred Education:** Intervention in these groups will be adopted from the successfully piloted SEDRIC study: A one-off three-hour workshop of structured group education (4-5 persons in each group) and three 2-weekly phone calls. Two educators will implement the session. Training for educators will involve completion of the DESMOND core training, reading and demonstrating understanding of the SEDRIC curriculum, and completion of at least two practice workshops that are

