##### Visit 1- First Assessment Visit:

At the first visit, participants will be assessed for eligibility and those eligible will be requested to consent for further screening. Baseline outcome measurements will be conducted including weight/height/HR/blood pressure, ABPI, Treadmill assessments, questionnaires and taking of blood sample ([name] and/or Research Nurse). Participants will be fitted with the activPAL™ monitor and advised to wear this continuously for seven days. They will be given an instruction on how to use the activPAL, and provided with a sleep diary to complete during the duration of wearing the activPAL.

First Assessment Visit (90 mins)	Time (mins)	Responsible
Review of Inclusion/Exclusion Criteria Obtain Informed Consent	20	RN/UA
Participant demographics 

Gender / Date of birth / Height / Weight / Heart rate / Blood pressure

 Patient history 

Diagnosis of PAD (Date of diagnosis/Type of disease)

Present drug history (Statin/Antiplatelet/Anticoagulants)

Past Medical History (IHD/MI/LVH)

Cardiac risk factors (DM/Family History of IHD,CVA/Smoking: Current, Previous, Non-smoker/Alcohol excess: Current, Previous, Never/Hypercholesterolemia/Hypertension

	20	
Complete questionnaires: 

Generic quality of life questionnaire (SF-36)

Intermittent Claudication Questionnaire (ICQ)

Visual Analogue Scale (VAS)

Geriatric Depression Scale (Short Form) (GDS-SF)

Pain Self-Efficacy Questionnaire (PSEQ)

Illness Perception Questionnaire (IPQ)

	20	
Taking of blood sample	10	
Treadmill protocol 

ABPI assessment

McGill Pain Questionnaire (MPQ) (5 minutes post-treadmill protocol)

	20	
Fitting of ActivPAL to participants and instruction for use	20	

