### Visit 2- Second Assessment Visit (usually within 2 weeks after visit 1):

Participants will then attend for a second visit to undergo a second Treadmill test, and to return the activPAL and sleep diary. Only participants with ≤20% variation in ACD will continue in the trial. After this visit eligible participants will be randomized, and given a date for them to return for intervention (TENS/Placebo ± Education) as applicable. Recruitment and randomisation will be done in waves to allow groups to be formed for the education session.

Second Assessment Visit (30 mins)	Time (mins)	Responsible
Return of ActivPAL by participants	5	RN/UA
Treadmill protocol • McGill Pain Questionnaire (5 minutes after completion of the treadmill protocol)	20	

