### Visit 3- Intervention Visit (within 3 weeks after randomisation):

Participants attend the clinic to receive the TENS and training instructions for its daily use as required, plus or minus the patient education per randomization group. Participants allocated to receive education will undergo a group structured education session (4-6 persons per group). This intervention is adopted from the successfully piloted SEDRIC study: a one-off three-hour workshop of structured group education followed by three 2-weekly phone calls (see SEDRIC curriculum).

The aim of the structured education is to modify patients' illness beliefs and perceptions about IC/PAD by educating them on disease pathology and management philosophy. After the workshop, each patient will be supported to set goals for walking based around a pedometer and daily steps, develop an action plan regarding how these goals will be met and encouraged to repeat this process for each new walking goal through a 2-weekly phone calls from the educators (research team- [name] and Research Nurse) during which the progress, barrier and challenges are further discussed, and new walking goal will be set.

Before the education session, participants allocated to receive TENS will be provided with the device and instruction to use of the device. Also, the use of the device will be demonstrated, and patients shown how to put on and remove the device. Participants will try it out so on that to be sure they understand the procedure.

Intervention Visit (as per randomisation) (approx. 4 hours)	Time (mins)	Responsible
1. Education session + Placebo TENS & instructions for the use at home	240	CS + RN
2. Education session + Active TENS & instructions for the use at home	240	
3. Active TENS and instructions for use at home	60	
4. Placebo TENS and instructions for use at home	60	

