### 7.2 Serious Adverse Event (SAE)

Any adverse event or adverse reaction that:

- a. results in death
- b. is life threatening
- c. requires hospitalisation or prolongation of existing hospitalisation
- d. results in persistent or significant disability or incapacity
- e. consists of a congenital anomaly or birth defect
- f. is otherwise considered medically significant by the investigator
- g. Important adverse events/ reactions that are not immediately life-threatening or do not result in death or hospitalisation but may jeopardise the subject or may require intervention to prevent one of the other outcomes listed in the definition above.

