### 7.3 Recording and reporting of Adverse Events

We do not anticipate that the use of the CE-marked TENS device will result in any serious adverse events. Participants will be given prior information regarding the reporting of adverse events and measure to take including instructions to contact the research team via a dedicated phone line.

Participants will be specifically queried regarding the following adverse events of special interest: any case of itching, skin breakdown, mild electrical burn, other skin allergies, or mild autonomic responses at each study visit, and reported related adverse events will be documented in an applicable adverse event form.

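### Adverse events are defined only in subjects already given a device, so events at the consented baseline treadmill tests are not clearly classed as AEs or SAEs

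*Protocol*

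**What the plan says.** **Definitions.** Protocol section 7.1 defines an AE as "Any untoward medical occurrence in a subject to whom a medicinal device has been administered" and adds that the product need not be the cause. Section 7.2 opens the SAE definition with "Any adverse event or adverse reaction that" and then lists seriousness criteria. An SAE must therefore first be an AE or a reaction.

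**Timeline.** Protocol section 4.1 places consent at Visit 1, where "those eligible will be requested to consent for further screening", and the first treadmill test is at the same visit. The section continues: "Participants will then attend for a second visit to undergo a second Treadmill test". The glossary makes the test of absolute claudication distance (ACD) maximal, since the patient goes on until symptoms force a stop. Randomisation comes after Visit 2 and is open only to those whose two ACD values vary by no more than 20%. On the device, the Interventions text of section 4 says: "Participants will be given TENS at intervention visit". That is Visit 3.

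**Recording and analysis.** Under section 7.3, participants are asked at every visit about itching, skin breakdown, mild electrical burns, other skin allergies and mild autonomic responses, and "reported related adverse events will be documented in an applicable adverse event form". Protocol section 8.5 and the SAP safety analysis summarise AEs by arm and in total. Neither mentions a period before randomisation.

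**The concern.** The riskiest procedure that participants undergo before treatment is a treadmill walk to maximal claudication pain, done twice. The protocol accepts that this carries risk, because section 3.3 excludes people with absolute contraindications to exercise testing. By then they have consented and are being tested only because the study requires it. Yet the wording of 7.1 and 7.2 attaches AE and SAE status to a device that, on the most natural reading, they do not yet have.

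If so, an event such as chest pain or a fall at a baseline test, even a serious one, has no place in the AE and SAE classification or in the safety summary. Safety is part of the feasibility question (Protocol section 2.3), and the same test supplies the outcome for sizing the definitive trial (section 4.2.2). Whoever plans that trial would want the test's safety record in everyone who took it.

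**Working it through.** The point rests on wording, and the plan gives no figure to reproduce. Two terms in 7.1 need a reading.

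**Step 1: which device?** TENS is the natural answer. Section 7.1 goes on to speak of a single product, section 6 (Device Information) describes only active and placebo TENS, and 7.3 names the TENS device. However, section 5 also calls the activPAL monitor a device when it warns of a "skin reaction to the adhesive in the strip used to attach the activPAL3 device to the thigh". The activPAL is fitted at Visit 1, and both the text and the table for that visit list the fitting after the treadmill test.

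**Step 2: when, or whose?** The clause can mean that events count once the device has been given, or that events count in people who are given it. The first is more natural for prospective recording. The second is possible because 7.1 states no onset date.

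**Step 3: combine the readings.**

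| Device | Clause says when events count | Clause says whose events count |
|---|---|---|
| TENS (Visit 3) | Tests at Visits 1 and 2 are outside | Randomised participants issued TENS are covered; people excluded at Visit 2 for ACD variation are outside |
| activPAL (Visit 1, after the test) | Test at Visit 1 is outside; test at Visit 2 is covered | Everyone fitted at Visit 1 is covered |

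The gap closes for those fitted only if the less natural reading is taken of both terms.

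**Step 4: does other text close it?**
- The 7.3 query applies at every visit, including Visits 1 and 2. Its list is limited to skin, mild burn and mild autonomic events, and only related events are written up. A cardiac event or a fall is not on it.
- The safety objective (section 2.2) concerns a specified set of events across the groups and sets no start at consent.
- Section 5 promises treadmill safety precautions, but no event reporting for the tests.
- The screening log (section 4.2.1), the withdrawal data (SAP Section 5) and the protocol deviations (SAP Section 4) may show that a test was cut short or that someone left. None of them classes the cause as an AE or SAE.

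**Step 5: exposure, for orientation only.** With 80 randomised (section 8.7) and all attending, tests before TENS number 2 x 80 = 160, and tests after it at most 2 x 80 = 160 (Visits 4 and 5). The share before TENS is at least 160/320 = 50%. If activPAL is the device, it is at least 80/320 = 25%. Visit 5 is only for those recruited in the first eight months. With no Visit 5 at all, the shares would be 160/240 = 67% and 80/240 = 33%. Tests in people excluded at Visit 2 would add to these, but the documents give no exclusion rate. These are counts of tests, not of events.

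**The case against.** The best defence is that 7.1 sets no time window. Every arm receives active or placebo TENS, so if the clause says whose events count, all randomised participants who receive a device are covered from the start. Section 7.3 gives this some support: a protocol that asks about AEs at every visit does not plainly mean that none can exist before Visit 3. This stands as a possible reading. It still leaves out those excluded at Visit 2 if the device is TENS.

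A second defence is scope. The safety objective and the summary are organised by group, groups do not exist before randomisation, and a focus on the intervention is defensible for a low-risk CE-marked device. That justifies keeping baseline events out of the by-arm table. It does not justify leaving them unclassified.

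Three stronger readings are tempting, and the documents do not support them:
- A reader might infer that a serious baseline event would go unreported. That is not shown. Section 7.3 sets out no SAE reporting route or timetable for any period, research governance procedures (section 11.0) apply but are not in the documents, trained staff deliver the assessments, and participants have a dedicated phone line.
- A reader might take the missing AE questionnaire in the Visit 1 and 2 tables as proof that baseline is excluded. The Visit 5 table, after device issue, has none either, so its absence proves nothing.
- A reader might take the 50% or 25% as a share of harm missed. The documents give no event rate, so these percentages should carry no weight.

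**Conclusion.** The point holds as a minor flaw in participant-safety wording. Nothing starts AE or SAE recording at consent. With TENS as the device and the clause read as a starting point, events at both baseline tests fall outside; with activPAL as the device, those at the Visit 1 test do. With TENS as the device, people excluded at Visit 2 fall outside under either reading of the clause.

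This rests on the listed order of procedures at Visit 1 being the order followed, and on no unseen procedure document setting an earlier start. No planned estimate changes: the by-arm safety comparison, the feasibility rates and the efficacy results are all unaffected. What is at stake is whether events at a study-required maximal test are classified and can be seen in the safety report.

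**What to change.** In Protocol sections 7.1 to 7.3, record AEs and SAEs in every participant from consent at Visit 1. Include events related to study procedures (treadmill test, activPAL, blood sampling) as well as to TENS. In section 8.5 and the SAP safety analysis, list events before Visit 3 descriptively for all consented participants, including those excluded at Visit 2, and keep that list separate from the by-arm summary.

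The cost is revised wording and a short extra listing. Study staff already run the baseline tests, so no visit, procedure or post is added. The downside is slightly more event logging and possibly a higher reported event count.
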